- Parts B and C will enroll subjects who are on NRTIs and have HBV DNA < 100 IU/mL at screening and have good hepatic reserve and a low level of hepatic inflammation at baseline as determined by the following attributes: ALT or AST $\leq 2 \times$ ULN, no history of hepatic decompensation, and lack of significant fibrosis and cirrhosis.
- Part D, which will enroll subjects who are not on NRTIs and have HBV DNA $\geq 1,000$ IU/mL and any HBsAg level, will be initiated only following SRC review of available safety data through the Week 4 visit for the cohort of subjects in Part B who are receiving a matching or higher dose.
- Two sentinel subjects will be randomized 1:1 to VIR-3434 or placebo and dosed. These sentinel subjects will be monitored through at least 72 hours post-dose and if the

investigator(s) have no safety concerns, the remaining 6 subjects in the same cohort will be dosed 5:1 (5 active and 1 placebo).

- Dose escalation will occur after SRC review of available safety data up to 4 weeks after dose administration to account for the anticipated timing of potential immune complex disease and hepatotoxicity due to the elimination of infected hepatocytes via ADCC/ADCP and/or cytotoxic T-cells induced via a vaccinal effect.
- Safety monitoring, including liver function tests, urinalysis, renal function, vital signs, and physical examination findings, is designed to detect evidence of VIR-3434-associated immune adverse events.

The risk/benefit assessment for subjects with chronic HBV is based on the balance between potential safety issues associated with the presence of antigen (HBsAg) and the anticipated benefits of a treatment modality designed to effectively reduce HBsAg, an immune tolerogen, and lead to clearance of infected hepatocytes. There is no approved therapy that reduces serum HBsAg in a substantial proportion of patients. If serum HBsAg can be effectively reduced in combination with clearance of infected hepatocytes, the anticipated safety profile of VIR-3434 would offer a favorable risk-benefit profile in patients with chronic HBV infection enrolled in Parts B, C, and D of the study.

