5.3.2. Part B Study Drug Dosing, Study Progression, and Dose Escalation

Overview: There are 5 planned cohorts in Part B: 6 mg SC (Cohort 1b), 18 mg SC (Cohort 2b), up to 75 mg SC (Cohort 3b), up to 300 mg SC (Cohort 4b), and up to 900 mg SC (Cohort 5b; Table 4). Cohort 1b will be the first cohort enrolled. Prior to initiating dosing of subsequent cohorts, the SRC will review available laboratory and clinical safety data and antiviral activity data through 4 weeks post-dose from the last available subject in the current Part B cohort prior to permitting dosing in subsequent cohorts. While these cohorts are planned to be enrolled

sequentially, they may be enrolled in parallel if the additional enrolled cohort(s) is examining a dose level which is at or below a dose level that has previously been found to have an acceptable safety and tolerability profile in Part A and Part B. Doses explored in Part B cohorts will not exceed the highest dose level in Part A that was determined to have an acceptable safety and tolerability profile by the SRC.

Initiation of Part B: Cohort 1b will be initiated after review of available safety data, inclusive of available Week 2 laboratory and clinical safety data, from Cohort 1a.

Optional Cohorts: Upon SRC review of available clinical and laboratory safety data and antiviral activity data, optional Cohort 6b and/or optional Cohort 7b may be enrolled and dosed at a lower, equivalent, or intermediate dose level relative to the dose levels explored in the planned Part B cohorts, or after cohort 5b at a dose level not exceeding 900 mg. The maximum dose level for the optional cohorts in Part B will also not exceed the highest single dose found to have an acceptable safety and tolerability profile in Part A. The optional cohorts may be enrolled at any time within the Part B planned cohorts based on the approval of the SRC. Enrollment of the Part B optional cohorts will be according to the same Part B eligibility criteria as the planned cohorts.

Table 4: Part B Cohort Overview

Study Part	Cohort	Route	Dose Level	Active:Placebo
B	1b	SC	6 mg	6:2
B	2b	SC	18 mg	6:2
B	3b	SC	up to 75 mg	6:2
B	4b	SC	up to 300 mg	6:2
B	5b	SC	up to 900 mg	6:2
B	6b (optional)	SC	up to 900 mg	6:2
B	7b (optional)	SC	up to 900 mg	6:2

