5.3.3. Part C Study Drug Dosing, Study Progression, and Dose Escalation

Overview: Part C is optional and may be conducted if VIR-3434 is found to have an acceptable safety and tolerability profile in HBeAg-negative subjects with HBsAg levels < 3,000 IU/mL in Part B. For cohorts in Part C, HBeAg-negative and HBeAg-positive subjects with HBsAg \geq 3,000 IU/mL will be enrolled.

There are 3 optional cohorts in Part C each evaluating up to 900 mg SC (Table 5). Cohort 1c will be the first cohort to initiate enrollment. Doses explored in Part C cohorts will not exceed the highest dose level in Part B that was determined to be safe by the SRC. Part C cohorts may be enrolled in parallel.

Initiation of Part C: Cohort 1c may be initiated after SRC review of available data for all subjects in Part A and Part B through the Week 4 visit for the cohort of subjects in Part B who are receiving a matching or higher dose.

Table 5: Part C Cohort Overview

Study Part	Cohort	Route	Dose Level	Active:Placebo
C	1c (optional)	SC	up to 900 mg	6:2
C	2c (optional)	SC	up to 900 mg	6:2
C	3c (optional)	SC	up to 900 mg	6:2

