- ^o Includes samples for ADA and neutralizing antibodies (NAb), as applicable. Additional unscheduled samples for immunogenicity analysis may be collected if an immunologic related event is suspected. Immunogenicity sampling beyond the planned follow-up period may occur based on emerging results. Further details can be found in Section 8.16 .
- ^p Local tolerability only needs to be assessed for subjects who are administered study drug by SC injection. On Day 1, local tolerability should be assessed at approximately 1 hour post-dose. At the discretion of the investigator, unscheduled visits are permitted as needed for follow up of any unresolved local tolerability symptoms.
- ^q All AEs related to screening activities must be collected starting at the time of consent; any other events occurring during the screening period should be reported as medical history. All SAEs must be collected from the time of consent onwards. Further details can be found in Section 9.3.

APPENDIX 3. PART B, C, AND D SCHEDULE OF ASSESSMENTS FOR SAD COHORTS IN SUBJECTS WITH CHRONIC HBV INFECTION WITHOUT CIRRHOSIS

Part B, C, and D														
Study Stage	Screening	Dosing Day ^a	Post-dose Follow-up Period							Extended Follow-up Period ^b				
Study Visit Week					W1		W2	W4	W8/ET ^c	W12	W16	W24	W32	W40 / EF ^d
Study Visit Day±Visit Window	D -42 to -1	D1 ^e	D2	D4+1	D8±1	D11±1	D15±2	D29±2	D57±7	D85 ±7	D113 ±7	D169 ±7	D225 ±7	D281 ±7
Informed consent	X													
Demography	X													
Medical history including HBV genotype ^f	X													
Inclusion/exclusion criteria	X	X ^g												
Full physical examination ^h	X			X					X					
Symptom-directed physical examination		X	X		X		X	X						
Body weight	X													
Height	X													
Vital signs ⁱ	X	X	X	X	X		X	X	X					
Safety ECGs ^j	X													
Pregnancy test ^k	X	X						X	X	X	X	X	X	X
FibroScan ^l	X													
Screening viral serology ^m	X													
Liver Function Tests ⁿ	X	X	X	X	X		X	X	X	X	X	X	X	X
Serum Chemistry ⁿ	X	X	X	X	X		X	X	X	X	X	X	X	X

Part B, C, and D														
Study Stage	Screening	Dosing Day ^a	Post-dose Follow-up Period							Extended Follow-up Period ^b				
Study Visit Week					W1		W2	W4	W8/ET ^c	W12	W16	W24	W32	W40 / EF ^d
Study Visit Day±Visit Window	D -42 to -1	D1 ^e	D2	D4+1	D8±1	D11±1	D15±2	D29±2	D57±7	D85 ±7	D113 ±7	D169 ±7	D225 ±7	D281 ±7
Hematology ⁿ	X	X	X	X	X		X	X	X					
Coagulation Parameters ⁿ	X	X	X	X	X		X	X	X					
Complement testing ^{n,o}		X			X		X							

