Urinalysis ^{n,o}	X	X			X		X							
Urine for drugs of abuse ^p	X													
Study drug administration ^q		X												
Blood samples for PK analysis ^r		X	X	X	X	X	X	X	X	X	X	X	X	X
Blood samples for immunogenicity analysis ^s		X					X	X	X	X	X	X	X	X
Blood sample for quantitative HBsAg	X	X	X	X	X	X	X	X	X	X	X	X	X	X
Blood sample for anti-HBs	X				X		X	X	X	X	X	X	X	X
Blood sample for HBeAg qualitative	X								X ^t					X ^t
Blood sample for HBeAg quantitative ^t		X						X	X					X
Blood sample for anti-HBe		X							X					X
Blood sample for HBV RNA quantitation and HBcrAg quantitation		X						X	X	X		X	X	X

Part B, C, and D															
Study Stage	Screening	Dosing Day ^a	Post-dose Follow-up Period							Extended Follow-up Period ^b					
Study Visit Week					W1		W2	W4	W8/ET ^c	W12	W16	W24	W32	W40 / EF ^d	
Study Visit Day±Visit Window	D -42 to -1	D1 ^e	D2	D4+1	D8±1	D11±1	D15±2	D29±2	D57±7	D85 ±7	D113 ±7	D169 ±7	D225 ±7	D281 ±7	
Blood sample for HBV DNA quantitation ^u	X	X	X ^v	X ^v	X	X ^v	X	X	X	X	X ^v	X	X ^v	X	
Blood sample for analysis of peripheral immune responses ^w		X			X		X	X	X	X		X		X	
Blood sample for RNA Paxgene tube ^x		X			X		X	X	X	X		X		X	
HBV resistance surveillance ^{u,y}		X			X		X	X	X	X	X	X	X	X	
Blood sample for Fc gamma receptor genotyping and for immunoglobulin allotyping		X													
CCI															
Local tolerability ^{aa}		X	X	X	X										
Review/record AEs ^{bb}	X									X					
Concomitant medications								X							
NRTI medication adherence ^{cc}								X							

AE = adverse event; ECG = electrocardiogram; EF = end of follow-up; ET = end of treatment; HBcrAg = hepatitis B core-related antigen; HBeAg = hepatitis B e-antigen; HBsAg = hepatitis B surface antigen; HBV = Hepatitis B Virus; NRTI = nucleoside/nucleotide reverse transcriptase inhibitor; PK = pharmacokinetic; SAD = single ascending dose

Note: When scheduled at the same timepoints, the assessments of vital signs and 12-lead ECGs must be performed before the blood sample collections.

- ^a Subjects may be admitted to the clinical investigative site on Day -1 or 1 and discharged after all study assessments are performed on Day 1. Patients must be monitored through at least 6 hours post-dose prior to discharge.

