- ^b Following Week 8, subjects with > 2-fold HBsAg reduction at Week 8 should be followed for up to 40 weeks or until the reduction in HBsAg is < 2-fold relative to baseline at 2 consecutive collections, whichever occurs first. The extended follow-up may be discontinued at the Sponsor's discretion based on emerging data.
- ^c If a subject withdraws participation prematurely from the study prior to the Week 8 visit, Week 8/ET assessments should be performed.
- ^d If a subject withdraws participation prematurely from the study after the Week 8 visit and prior to the Week 40 visit, Week 40/EF assessments should be performed.
- ^e Assessments performed predose unless otherwise specified.
- ^f A complete medical history will be taken at screening. Any changes should be updated prior to dosing. HBV genotype information will also be collected, if available. For subjects with HBV DNA > 500 IU/mL, viral sequencing from the HBV resistance surveillance sample may be used to determine genotype.
- ^g Prior to study drug administration on Day 1, subject eligibility will be confirmed.
- ^h See Section 8.3 for assessments to be performed during a full physical examination.
- ⁱ Vital signs (blood pressure, pulse rate, respiratory rate and temperature [oral preferred]) should be measured after the subject has rested comfortably for approximately 10 minutes. On Day 1, vital signs should be measured within 2 hours prior to dose, at 2 hours post-dose (+/- 1 hour), and at 6 hours post-dose (+/- 1 hour). On all other visit days, vital signs are only required to be recorded once during the visit.
- ^j ECGs should be measured in the supine position after the subject has rested comfortably for approximately 10 minutes.
- ^k WOCBP are required to have pregnancy tests. A blood pregnancy test will be performed at screening and a urine pregnancy test will be performed thereafter. Negative pregnancy test must be confirmed prior to study drug administration.
- ^l Does not need to be performed if the subject has had a FibroScan in the 6 months prior to screening or liver biopsy in the year prior to screening that confirmed the absence of Metavir F3 fibrosis or F4 cirrhosis.
- ^m See Section 8.10 for viral serology parameters.
- ⁿ Clinical laboratory and urinalysis parameters are described in Appendix 9.
- ^o Additional samples may be collected at any time post-dosing if immune-complex disease is suspected.
- ^p Drugs of abuse included in the screen are described in Section 8.14.

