6.4.2. Clinical Laboratory

Clinical laboratory data collected (through central laboratories only, unless otherwise specified) will be analyzed using both quantitative and qualitative methods and presented by VIR-3434 treatment cohort and placebo, for each of Part A, B, C, and D. The analysis will be based on values reported in conventional units.

For the treatment-emergent laboratory measurements, the observed values and change from baseline values of the continuous hematology, serum chemistry, and coagulation results will be summarized descriptively (n, mean, SD, median, min, max) at each visit.

For ALT, AST, total bilirubin, lymphocytes, neutrophils, platelets, and INR, mean (\pm SD) of the observed values will be plotted by visit and by each VIR-3434 treatment cohort and placebo for each of Part A, B, C, and D.

The Common Terminology Criteria for Adverse Events (CTCAE, v5.0) will be used as the reference on grading scale to assign severity (toxicity) grades (1 to 4) to abnormal results for the laboratory of interest as shown in Appendix 5. Grade 0 refers to the normal values that do not meet the criteria of laboratory abnormalities.

For treatment-emergent laboratory abnormalities, the number and percentage of participants who met at least 1 threshold criterion of severity grade will be summarized by VIR-3434 treatment cohort and placebo for each of Part A, B, C, and D, based on the most severe postdose abnormality grade during TE period for a given laboratory test. The threshold of severity grade shifted from baseline will also be summarized for selected laboratory tests.

In addition, a separate listing containing individual participants with hematology, chemistry, coagulation, and urinalysis values will be provided based on the Safety Analysis Set by subject ID and visit in chronological order including data collected from both scheduled and unscheduled visits. Values falling out of the relevant normal range (between the value of LLN and ULN) or having the severity grade of 1 or higher on laboratory abnormalities will be flagged as appropriate.

Results of positive urine/serum pregnancy test will be listed in an individual participant data listing only.

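### Scheduled urinalysis and complement testing end at Week 2, yet Section 2.4 ties the 4-week review before Part B escalation partly to the timing of immune complex disease and names urinalysis as a detection tool

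*Protocol*

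**What the plan says.** Protocol Section 2.4 names immune complex disease and hepatotoxicity as the target-related risks in subjects with chronic HBV infection. Among the mitigations it states: "Dose escalation will occur after SRC review of available safety data up to 4 weeks after dose administration to account for the anticipated timing" of those two risks. The next bullet reads: "Safety monitoring, including liver function tests, urinalysis, renal function, vital signs, and physical examination findings, is designed to detect evidence of VIR-3434-associated immune adverse events".

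Section 5.3.2 makes the review operational for Part B: before later cohorts are dosed, "the SRC will review available laboratory and clinical safety data and antiviral activity data through 4 weeks post-dose from the last available subject" of the current cohort. Sections 5.3.3 and 5.3.4 allow Parts C and D to open after review of Part B data through Week 4 at a matching or higher dose. They set no 4-week wait between their own cohorts; for Part C, "Part C cohorts may be enrolled in parallel".

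Appendix 3 schedules complement at Day 1, Week 1 and Week 2, and urinalysis at screening, Day 1, Week 1 and Week 2. Neither is marked at Week 4 or Week 8. A footnote to both rows says: "Additional samples may be collected at any time post-dosing if immune-complex disease is suspected". SAP Appendix 2, Table 7-1, also has Week 2 as the last urinalysis visit in Parts B to D.

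For reporting, SAP Section 6.4.2 says that "continuous hematology, serum chemistry, and coagulation results will be summarized descriptively" by visit. Urinalysis is listed only, and complement is not mentioned.

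**The concern.** The length of the review is justified partly by when immune complex disease is expected, and urinalysis is one of the tests said to detect immune events. The schedule stops that test halfway through the period. A reader of Section 2.4 would assume that the Week 4 data include a urine result from about Week 4. Under Appendix 3 they do not, unless someone already suspected disease.

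Safety is the primary objective, and this review is the safeguard before each higher Part B dose and before Parts C and D open. At stake is what a clean Week 4 review can be taken to mean. For urine and complement it means clean at Week 2, plus no clinical suspicion afterwards.

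**Working it through.** No statistical figure in the plan is involved. The check sets the passages side by side and adds simple date arithmetic.

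**1. Scheduled tests (Appendix 3) against the monitoring named in Section 2.4**

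| Element | Week 1 | Week 2 | Week 4 | Week 8 |
|---|---|---|---|---|
| Liver function tests | yes | yes | yes | yes |
| Renal function (serum chemistry) | yes | yes | yes | yes |
| Vital signs | yes | yes | yes | yes |
| Physical examination | symptom-directed | symptom-directed | symptom-directed | full |
| Urinalysis | yes | yes | **no** | **no** |
| Complement (not named in 2.4) | yes | yes | **no** | **no** |

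Four of the five named elements are present at Week 4. Urinalysis is the one that is missing.

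**2. Length of the gap**

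The Week 2 visit is Day 15 ±2 and the Week 4 visit is Day 29 ±2.
- Nominal: 29 − 15 = 14 days
- Shortest: 27 − 17 = 10 days
- Longest: 31 − 13 = 18 days
- Share of the 4-week period: 14 / 28 = 0.5

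**3. Can the remaining Week 4 data show an asymptomatic change?**
- Adverse events: Protocol Sections 9.1.1 and 9.1.3 exclude laboratory abnormalities that have no signs or symptoms and need no intervention.
- Examination: Section 8.4 leaves the symptom-directed examination to the investigator's discretion.
- Serum chemistry: Appendix 9 includes creatinine, urea nitrogen and creatinine clearance. Urine protein and red cells appear only under urinalysis.
- For-cause samples: these are optional and need prior suspicion.

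Symptomatic disease, or disease that alters serum renal markers, can be seen. Silent proteinuria, haematuria or complement consumption is not routinely looked for. Appendix 8 lists urinalysis and complement among the samples to consider when immune complex disease is suspected, so the protocol itself treats both as informative.

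**4. What the SAP would report**
- SAP Section 6.4.2 has no by-cohort summary of urinalysis or complement, and the grading table in SAP Appendix 5 contains neither.
- The Appendix 3 footnote sends the reader to Protocol Appendix 9 for parameters, but Appendix 9 lists no complement component.
- In Table 7-1 the Week 2 urinalysis window opens after Day 11 and has no later visit to close it before the end of main follow-up. A for-cause urine sample near Day 29 would be labelled Week 2, where the table notes give a scheduled result precedence.

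**5. Subjects concerned, by design**

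SAP Table 2 marks four Part B cohorts as enrolled (6, 18, 75 and 300 mg), which makes three escalation steps. At 6 active and 2 placebo per cohort, 4 × 8 = 32 subjects, 24 of them active, supply the Part B data. Three Part C and two Part D cohorts are also marked enrolled under the same schedule: 9 × 8 = 72 subjects in all, 9 × 6 = 54 active.

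**The case against.** The strongest reply is that Section 2.4 promises a review of available data up to 4 weeks, not a repeat of every test at Week 4. The 4-week period also serves hepatotoxicity, for which liver tests are scheduled at Week 4. Appendix 8 gives joint and skin findings as the most common manifestations of immune complex disease, and clinical follow-up would catch those. All adverse events are collected through Week 8, and for-cause urine and complement samples are allowed at any time. Section 2.4 never names complement, so its absence at Week 4 contradicts nothing there. The committee's data requirements are in a charter that is not among these documents.

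Most of this stands. It rules out several stronger readings that a reader might draw:
- That the Week 4 review lacks the tests that would show the disease. It does not: four of five named elements are there, along with the Week 1 and Week 2 urine and complement results.
- That a 4-week wait separates cohorts throughout Parts B to D. The rule in Section 5.3.2 is for Part B.
- That the gap is worst in Part C because antigen load is highest there. Part C has a minimum HBsAg of 3,000 IU/mL, but Part D admits any level.
- That the predicted pharmacokinetics in Section 2.3.2 can size the risk. That model is linear, scaled from monkeys, and has no antigen term, so it cannot say when complexes form.

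On the SAP, Section 6.4 says all safety data will be listed, and Protocol Section 10.4.2 promises summaries only of selected laboratory data. Complement would therefore appear in a listing at least, and listing urinalysis is a permissible choice.

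The reply does not remove the mismatch on urinalysis. Section 2.4 names it as a detection tool beside a 4-week review, and Appendix 3 ends it at Week 2.

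**Conclusion.** The point holds in this limited form. For urinalysis, Section 2.4 and Appendix 3 do not agree: the scheduled test covers the first half of the period whose length is partly justified by immune complex disease. Complement has the same gap, as an observation about coverage rather than a contradiction.

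The size is 14 of 28 days (10 to 18 days with windows), in Part B data from 32 subjects by design. It concerns asymptomatic changes only. The documents do not say that immune complex disease is expected specifically between Weeks 2 and 4, so how many events could be missed cannot be estimated. The conclusion assumes that the schedule was followed as printed and that neither the committee's charter nor the redacted parts of Appendix 3 and the SAP add such samples. It is worth correcting because it touches a safeguard that gates escalation and costs little to put right.

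**What to change.** Reconcile Protocol Section 2.4 with Appendix 3. There are two ways, and the choice is the sponsor's:
- Align scheduled urinalysis and complement with the Week 4 review at a visit that already exists. The cost is one urine test and one tube per subject, and a few incidental findings to follow up.
- Restate Section 2.4 so that the review is not described as having urine or complement coverage beyond Week 2. The cost is an edit to the text.

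The SAP already marks nine Part B to D cohorts as enrolled, so the first option may come too late for them. The wording and reporting changes still apply.

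In either case, before database lock:
- Add to SAP Section 6.4.2 a by-cohort descriptive summary of complement change from baseline and of new urine protein or blood abnormalities. Name the complement components measured.
- Count new urine abnormalities at any post-baseline time, including unscheduled samples, so that the open Week 2 window does not hide a later for-cause result. SAP Section 6.1 already uses unscheduled values when deriving maxima and minima.
- In reports, state the last scheduled urine and complement sample, and claim no routine coverage after it.

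This is one descriptive table and a sentence of reporting text.
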